Secondary Outcome Measures:	
 1) Erythrocyte protoporphyrin over time: Mean values and standard deviations will be computed at each time point and values will be compared descriptively. Additionally, a random effects longitudinal model of erythrocyte protoporphyrin with time as the predictor variable will be fit and used to assess whether subjects' erythrocyte protoporphyrin varied with time. 2) EPP-specific QOL: Mean scores and standard deviations will be computed at each time point and values will be compared descriptively 3) Safety: Rates of Adverse events will be computed and safety variables such as physical and other laboratory findings will be analyzed descriptively.
Statistical Considerations (sample size and analysis plan):	
A Bayesian approach based on the posterior distribution that the mean relative difference between baseline and 12-month erythrocyte protoporphyrin levels is greater than 0 will be used to assess the strength of potential efficacy. The posterior probability that the relative difference is greater than 0 will be computed. A probability $\geq 80\%$ (corresponding to an approximate quadrupling of the odds that iron is effective in lowering erythrocyte protoporphyrin) will be considered evidence that additional study of iron is warranted.
 
Assuming the distribution of baseline erythrocyte protoporphyrin is gamma (2.3, 861) and that baseline and 1 year values are correlated with $r = 0.7$, simulations indicate that a total sample size of 20 patients will allow us to detect an approximate quadrupling of the odds that iron is effective in lowering erythrocyte protoporphyrin if the true effect size is 10%.

Sponsors (federal, state, foundation and industry support):	National Institutes of Health (NIH)

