The Office of Rare Diseases (ORD) of the National Institutes of Health (NIH) established a Rare Diseases Clinical Research Network (RDCRN) in collaboration with other NIH Institutes and has funded several rare diseases clinical research consortia and one Data Management and Coordinating Center. The Porphyrias Consortium was created as part of the RDCRN, to study the human porphyrias. The Porphyrias Consortium is a consortium of the academic institutions listed in the participating institutions table. All Centers in the Porphyrias Consortium are participating in this study. Additional centers may be added if funding is available.

2. Specific Aims (Hypothesis and Objectives)

The overall objectives of this study are to determine the efficacy and safety of oral iron administration in the protoporphyrrias. Efficacy will be based on erythrocyte protoporphyrin levels, photosensitivity, other clinical symptoms, and quality of life in patients with EPP and XLP who have diminished iron stores (serum ferritin ≤ 30 ng/ml).

Primary Objective: To determine if oral iron therapy can decrease erythrocyte protoporphyrin levels in patients with EPP and XLP.

Secondary Objectives:

- 1) To assess whether oral iron therapy can improve iron status and decrease plasma porphyrin levels and clinical symptoms
- 2) To assess if there is an improvement in the quality of life in treated patients

This is an open label pilot study of the safety and efficacy of oral iron therapy in patients with EPP and XLP with diminished iron stores as defined by serum ferritin level.

3. Background

Erythropoietic Protoporphyrinia (EPP) is characterized by painful, non-blistering, cutaneous photosensitivity, with onset in early childhood. EPP is the most common porphyria in children and the third most common in adults (after porphyria cutanea tarda and acute intermittent porphyria). Reports of prevalence vary between 5 and 15 cases per million population. (2-4)

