The role of iron replacement in EPP and the clinical response to increased iron is controversial, some reports suggest clinical improvement (12, 13, 14, 15) while others describe an exacerbation of photosensitivity (16, 17). Notably, an increase in protoporphyrin levels, has never been documented, in EPP patients treated with iron. Based on these conflicting reports, clinical practice varies among physicians with some using oral iron replacement in EPP patients with low iron stores and others choosing no intervention. No results or follow up on the effectiveness of oral iron therapy have been reported. A recent report from the U.K. showed clinical and biochemical improvement in a single EPP patient that had been treated with low doses of intravenous iron (17). Hemin therapy has also been used in EPP patients with advanced liver disease prior to transplantation and decreases in erythrocyte and plasma protoporphyrin levels have been observed (18). Although the mechanism of action is unclear, a possible hypothesis is that hemin, which contains iron, improves iron stores in these patients by providing iron, as well as bypassing the deficient *FECH* enzyme, leading to a decrease in protoporphyrin levels. Results from previous studies of the natural history of EPP/XLP

suggest that there is little change in erythrocyte protoporphyrin levels over time and there is little intra-individual variation (11).

Interestingly, oral iron replacement in one patient with XLP with diminished iron stores also led to a decrease in erythrocyte protoporphyrin levels (2). We also administered oral iron to a patient with XLP and observed a 20% decrease in erythrocyte protoporphyrin levels. We have now enrolled a large number of patients in an EPP Natural History study, several of whom were treated in the past with oral or intravenous iron therapy and experienced improvements in iron status without adverse consequences before they entered our studies. Unfortunately, serial measurements of protoporphyrin levels were not done prior to enrollment in our longitudinal studies. While these reports and our experience to date suggest that iron replacement can improve iron status and may decrease erythrocyte protoporphyrin levels, the efficacy and safety of iron therapy in EPP and XLP have not been systematically investigated, and whether or not to use iron in these patients remains an unanswered clinical question.

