4.1 Inclusion Criteria

1. Enrollment in the Longitudinal Study of the Porphyrias (7201)
2. Male or female age ≥ 18 years
3. Willing to sign informed consent form and follow protocol
4. History of nonblistering cutaneous photosensitivity
5. Biochemical findings - A marked increase in erythrocyte protoporphyrin (total erythrocyte protoporphyrin >400 ug/dL) with a predominance of metal-free protoporphyrin
6. Serum ferritin ≤ 30 ng/mL at baseline
7. Able to tolerate oral iron

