5.9 Quality Control: Study Related Procedures

The standard laboratory measures (CBC, CMP, Iron panel, etc) will be performed at each sites' central laboratory. Erythrocyte protoporphyrin measurements will be performed in the CLIA certified laboratory of [name], University of Texas Medical Branch, Galveston, TX.

The investigational pharmacy at each site will be responsible for drug accountability while the investigators/coordinators will be responsible for compliance of the subjects. The Investigational Drug Service at the Icahn School of Medicine at Mount Sinai will serve as the coordinating pharmacy for this study.

6. Statistical Considerations

The primary outcome is the relative difference in erythrocyte protoporphyrin levels between baseline and 12 months after treatment. A Bayesian approach based on the posterior distribution that the mean relative difference between baseline and 12-month erythrocyte protoporphyrin levels is greater than 0 will be used to assess the strength of potential efficacy of oral iron therapy.

The procedure will be carried out as follows. Let X_0 and X_{12} be the observed mean erythrocyte protoporphyrin level at baseline and 12 months. Let X_0 and X_{12} be correlated with a Pearson correlation coefficient of r and let $d = \frac{X_0 - X_{12}}{X_0}$ and $\Theta = \frac{\mu_0 - \mu_{12}}{\mu_0}$.

Based on data observed in previous studies, we assume that the distribution of

erythrocyte protoporphyrin follows a gamma distribution (see background data section below). For an individual i , $X_{0i} \sim \text{gamma}(\alpha_0, \beta_0)$ and $X_{12i} \sim \text{gamma}(\alpha_{12}, \beta_{12})$.

$X_0 = \frac{\sum_{i=1}^n (X_{0i})}{n}$, therefore $\frac{1}{n} X_0 \sim n * \text{gamma}(\alpha_0, \beta_0) = \text{gamma}(n\alpha_0, \beta_0)$ and likewise $\frac{1}{n} X_{12} \sim \text{gamma}(n\alpha_{12}, \beta_{12})$.

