Two correlated gamma distributions can be generated using a single parameter α , the means of each distribution and the standard deviation as detailed in Ronning et al (23). We specify a non-informative normal($n^*0, 0.01$) prior for α . After data collection the posterior distribution of $\alpha|d \sim \text{normal}(n^* \frac{X_0}{\sigma_0^2/X_0}, 0.01)$. The posterior distribution for $\Theta|d$ can be generated by simulating baseline and 12 month mean values using the posterior distribution of $\alpha|d$, the observed correlation between 12 month and baseline values and the observed standard deviations. After generating the posterior distribution for $\Theta|d$ we will be able to compute the probability that $\Theta|d > 0$.

Prior to any data collection, equipoise implies that the probability that iron therapy will improve erythrocyte protoporphyrin levels (i.e. the relative difference between baseline and 12 months will be greater than 0) is 50%. An increase in this probability to a level providing reasonable assurance of an efficacy signal (e.g. 80%) would warrant additional study of iron. A probability of 80% corresponds to an approximate quadrupling of the odds that iron is effective in lowering erythrocyte protoporphyrin (i.e., from 50% probability of iron's efficacy, or 1:1 odds, to 80% or 4:1 odds).

Sample size justification:

Assuming the distribution of baseline erythrocyte protoporphyrin is gamma (2.3, 861) and that baseline and 12 month values are correlated with $r = 0.7$, simulations indicate that a total sample size of 20 patients will allow us to detect an approximate quadrupling of the odds that iron is effective in lowering erythrocyte protoporphyrin if the true effect size is 10%. Table 2 lists simulated estimates (100,000 runs for each) of the probability that $\Theta|d > 0$ across several sample size and effect size scenarios.

Table 2: Simulation results

r	Sample Size	Effect Size				
		0%	5%	10%	15%	20%
.7	10	0.50	0.63	0.74	0.83	0.90
	15	0.50	0.65	0.78	0.88	0.94
	20	0.50	0.67	0.81	0.91	0.96
	25	0.50	0.69	0.84	0.93	0.97
	30	0.50	0.71	0.86	0.95	0.98
	35	0.50	0.72	0.88	0.96	0.99
	40	0.50	0.74	0.89	0.97	0.99

Background Data

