As of March 17, 2015 there were 152 EPP and XLP patients in The Longitudinal Study of the Porphyrias who had an erythrocyte protoporphyrin level >400 , were not on Iron therapy and had no reported liver disease (fibrosis, cirrhosis, steatosis) or liver transplant history. The distribution of these patients' baseline erythrocyte protoporphyrin is pictured in figure 2.

[figure not shown]

Figure 2: Distribution of 152

Data from The Longitudinal Study of the Porphyrias demonstrated that the correlation between erythrocyte protoporphyrin levels taken approximately 1 year apart was 0.74.

Secondary Analyses:

In addition to the primary outcome, the following secondary endpoints will be analyzed:

- 1) Erythrocyte protoporphyrin over time: Mean values and standard deviations will be computed at each time point and values will be compared descriptively. Additionally, a random effects longitudinal model of erythrocyte protoporphyrin with time as the predictor variable will be fit. Time will be treated as a continuous measure unless diagnostic plots suggest that a linear mean function for time is not the correct specification. If this is the case, time (ie visit timepoint) will be treated as a categorical variable. Using the fitted model, we will test the null hypothesis that the beta coefficient(s) for time = 0. There have been no previous studies on the effect of iron therapy on erythrocyte protoporphyrin over time. As such, no estimates of between-subject variability or effect size are available to pre-specify the power of this analysis.

- 2) EPP-specific QOL overtime: To assess whether the subjects' EPP-specific QOL changed during the duration of the study, the mean score and standard deviation will be computed at each time point and compared descriptively.
- 3) Safety Endpoints: Rates of Adverse events will be computed. Safety variables such as physical and other laboratory findings will be analyzed descriptively.

7. Data Management

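### The 80% posterior measures whether mean protoporphyrin fell, not whether iron lowered it: reword it and report the untreated one-year change from study 7201 beside it

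*Combined protocol and SAP*

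**What the plan says.** Section 2 (Specific Aims) describes the design: "This is an open label pilot study of the safety and efficacy of oral iron therapy". Section 4.8 has every participant treated for a year, so there is no concurrent untreated group.

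Section 6 defines the endpoint: "The primary outcome is the relative difference in erythrocyte protoporphyrin levels between baseline and 12 months after treatment". Formally, Theta = (mu0 − mu12)/mu0, and the analysis computes the posterior probability that Theta exceeds zero. The paragraph on equipoise then treats this as a statement about iron, giving 50% as the prior probability that "iron therapy will improve erythrocyte protoporphyrin levels (i.e. the relative difference between baseline and 12 months will be greater than 0"). It reads 80% as odds of 4:1 that iron lowers protoporphyrin. The Synopsis repeats this reading and says that such a result "will be considered evidence that additional study of iron is warranted".

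On the untreated course, Section 3 says that earlier natural-history studies "suggest that there is little change in erythrocyte protoporphyrin levels over time and there is little intra-individual variation", with a citation but no figure. Under Background Data in Section 6, the plan draws on the parent Longitudinal Study (7201), in which every trial participant must be enrolled: "there were 152 EPP and XLP patients in The Longitudinal Study of the Porphyrias who had an erythrocyte protoporphyrin level" above 400, were off iron and had no reported liver disease. From the same study, "the correlation between erythrocyte protoporphyrin levels taken approximately 1 year apart was 0.74". The mean one-year change is not given, and Section 6 plans no use of it.

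**The concern.** Theta has no term for what would have happened without iron. The probability that Theta exceeds zero equals the probability that iron lowered protoporphyrin only if the untreated mean change is zero. The plan makes that step by definition, without stating it as an assumption or giving a number for it. The planned longitudinal model does not help, because it tests a time effect in the same treated patients.

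The result decides whether iron is studied further, and odds that iron works is the phrase a reader will take from it. The figure that would help a reader judge that phrase is the mean one-year change off iron. It should be obtainable from the study that already supplied the one-year correlation.

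**Working it through.** **Inputs.** Section 6: baseline gamma(2.3, 861), r = 0.7, n = 20, Table 2, 7201 correlation 0.74, 152 patients. Section 3: 52% of 7201 patients with low ferritin (cut-off not stated). Section 4.1: protoporphyrin above 400 ug/dL.

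**1. Reproduce Table 2.** Mean = 2.3 × 861 = 1980; SD = √2.3 × 861 = 1306; CV = 0.659. The SE of the relative difference is 0.659 × √(2 × 0.3/20) = 11.4 points. Phi(effect/11.4) at 0, 5, 10, 15 and 20% gives 0.50, 0.67, 0.81, 0.91 and 0.96, which is the n = 20 row. Nothing in this calculation refers to the cause of the fall.

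**2. Fall that meets the rule.** 0.842 × 11.4 = 9.6%. Interpolating Table 2 between 5% (0.67) and 10% (0.81) gives 5 + 5 × 0.13/0.14 = 9.6%.

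**3. Chance of meeting the rule when iron does nothing.** Phi(g/11.4 − 0.842), where g is the mean fall without iron. The 2% and 5% values are assumptions, since the documents give none.

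| Untreated fall g | Normal approximation | Correlated-gamma simulations |
|---|---|---|
| 0% | 20% | 21–22% |
| 1.2% | 23% | 24–26% |
| 2% | 25% | 27–28% |
| 5% | 34% | 36–38% |

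The first row belongs to the 80% threshold itself and has nothing to do with drift.

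**4. The one source of drift that can be sized.** Selecting on a baseline above 400 produces some regression to the mean. Under the gamma, 4.6% of values lie below 400 and the mean above 400 is 2064. The expected fall is (1 − 0.7) × 83/2064 = 1.2%. This is an upper figure, because the 152 patients shown as background data were already limited to values above 400. Selection on low ferritin might also matter, but the documents give nothing from which to size it.

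**5. What the correlation adds.** A correlation is unchanged if every value shifts or scales by the same amount, so 0.74 carries no information on mean change.

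**6. Precision of an untreated estimate from 7201.** With r = 0.74, SE = 0.659 × √(0.52/m) for m pairs.

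| Pairs m | SE (points) | 95% half-width | Chance the interval excludes 0 if the true fall is 5% | Chance of an observed change of 5 points or more if the true change is 0 |
|---|---|---|---|---|
| 152 | 3.86 | ±7.6 | 25% | 19% |
| 79 | 5.35 | ±10.5 | 15% | 35% |
| 20 | 10.63 | ±21 | 8% | 64% |

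The true m is not given. 152 assumes that every patient has a one-year pair, 79 also applies the 52% (0.52 × 152), and 20 is illustrative. A half-width of 5 points would need 0.52 × (1.96 × 0.659/0.05)² = about 347 pairs, more than the 152 patients listed.

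**The case against.** The case for leaving the text alone has force. The plan speaks of potential efficacy and an efficacy signal, calls itself an open-label pilot, and uses the 80% only to decide on more study. Section 3 does address the untreated course, and its cited source may hold a figure. I also did not have the text between Figure 1 and Section 4.1. If levels are stable, a fall is close to the iron effect. All this softens the problem, but it does not turn a change from baseline into odds that iron works, and that is how two places in the plan describe it.

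Three stronger readings are tempting, and the documents do not support them.

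- A reader might infer that untreated levels drift downward and that the result will be biased. No drift is shown, and the only part that can be sized is about 1.2%.
- A reader might take the 34–38% as a false-positive rate caused by the missing control. It rests on an assumed 5% fall, and 20–22 points of it are present with no drift at all.
- A reader might expect the 7201 data to apportion a fall between iron and background, for instance through a probability that the fall on iron exceeds the untreated fall. The data are too noisy. Beside a trial fall of 9.6%, with 79 pairs and no true drift, chance alone gives an untreated change of 5 points or more 35% of the time. That would move such a probability to 0.64 or lower, or 0.88 or higher.

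**Conclusion.** The point holds as one of description and reporting. The plan's probability is correctly defined as a probability of a fall from baseline and then mislabelled as a probability about iron. The label is right only if the untreated mean change is zero, which the available text supports with one statement lacking a number. The size of any error is unknown. The part that can be estimated raises the chance of meeting the rule without an iron effect from about 20% to at most about 23%. These figures rest on the plan's gamma baseline, r = 0.7, n = 20 with no dropout, and a normal approximation that reproduces Table 2. The primary analysis, the 80% rule and the sample size can stand.

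**What to change.** **Wording.** In the Synopsis and Section 6, describe the 80% as the probability that mean protoporphyrin fell from baseline to 12 months, attributable to iron only in so far as untreated levels are stable.

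**Supporting report.** Add to Section 6, for example:

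> Descriptive supporting analysis: among 7201 participants who took no iron at either visit or in between and who, at the first visit, met the trial's main entry limits as far as 7201 records them (adult, erythrocyte protoporphyrin >400 ug/dL, ferritin ≤30 ng/mL, no liver disease), the mean relative change over about 12 months will be reported with its 95% interval, the number of pairs and the assay laboratory. Each person contributes one pair. The time window will be fixed before the data are examined. The 80% rule is not altered.

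I would report the untreated change and its interval only, without a formal probability comparing it with the trial.

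**Cost.** Some SAP text and one analysis of parent-study data; trial conduct does not change. The comparison is not randomised, the number of usable pairs is unknown, and the wide interval can reveal a large drift but cannot rule out 2–5%. The wording change needs no data and is worth making even if few pairs exist.

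### Table 2's 0.81 is not the chance of meeting the plan's 80% criterion; with 20 patients and a true 10% reduction that chance is about 0.51 to 0.58

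*Combined protocol and SAP*

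**What the plan says.** The decision rule is in the Synopsis (Statistical Considerations): a posterior probability of at least 80% that the mean relative difference exceeds zero "will be considered evidence that additional study of iron is warranted". Section 6 gives the same rule a little more loosely: a "level providing reasonable assurance of an efficacy signal (e.g. 80%) would warrant additional study of iron". Both places equate 80% with moving from 1:1 to 4:1 odds.

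The sample size statement follows from that rule. Section 6 says that "a total sample size of 20 patients will allow us to detect an approximate quadrupling of the odds that iron is effective" when the true effect is 10%, and the Synopsis makes the same claim ("simulations indicate that a total sample size of 20 patients will allow us to detect"). The evidence is described as follows: "Table 2 lists simulated estimates (100,000 runs for each) of the probability that" the relative difference exceeds zero, by sample size and effect size, at a correlation of 0.7. The entry for 20 patients and 10% is 0.81. Under Background Data, the same section reports that the "correlation between erythrocyte protoporphyrin levels taken approximately 1 year apart was 0.74".

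**The concern.** A claim that a trial of a given size will detect something is a claim about how often its decision rule will be met. Here the rule is a posterior probability of 80% or more, so the relevant figure is the proportion of 20-patient trials that reach 80% when the true reduction is 10%. Table 2 reports a different quantity, and its 0% column shows this: it reads 0.50 at every sample size, whereas a rule that asks for 80% would be met in about 20% of trials with no effect.

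This sentence is the only justification given for 20 patients. A reader is likely to take it that a true 10% reduction would usually trigger the go decision. If it does so only a little over half the time, a posterior below 80% could be read as no signal when a real 10% reduction is present. Those approving the trial also cannot see how often an ineffective treatment would be carried forward.

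**Working it through.** **Inputs.** From the sample size justification in Section 6: baseline gamma(2.3, 861), correlation r = 0.7, n = 20, true effect 10%. From Background Data in Section 6: observed r = 0.74. From the Synopsis: threshold 0.80. The month-12 SD is not stated, so two assumptions are used: equal to the baseline SD, or scaled down with the mean.

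**Step 1: standard error of the relative difference.**
- Mean = 2.3 × 861 = 1980.3; SD = √2.3 × 861 = 1305.8; CV = 1305.8 / 1980.3 = 0.6594.
- With equal SDs, SE = CV × √(2(1 − r)/n).
- r = 0.7: 0.6594 × √(0.60/20) = 0.1142.
- r = 0.74: 0.6594 × √(0.52/20) = 0.1063.

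**Step 2: reproduce Table 2.** Take Φ(effect/SE) at r = 0.7. For n = 20:

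| Effect | 0% | 5% | 10% | 15% | 20% |
|---|---|---|---|---|---|
| Φ(effect/SE) | 0.500 | 0.669 | 0.809 | 0.905 | 0.960 |
| Table 2 | 0.50 | 0.67 | 0.81 | 0.91 | 0.96 |

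Over all 35 cells the largest difference is 0.0084. The printed values therefore match the posterior probability under a flat prior when the observed reduction equals the true one. Numerically this is also the chance that the observed mean falls at all. Two other readings do not fit the cell for 20 patients and 10%: the posterior averaged over trials would be about 0.73 to 0.75, and the chance of reaching 80% is the figure in Step 3.

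**Step 3: chance of meeting the criterion.** With a flat prior, a posterior of at least 0.80 requires d/SE ≥ 0.8416. Hence P(criterion met) = Φ(effect/SE − 0.8416).
- r = 0.7, 10%: 0.10/0.1142 = 0.8756, and Φ(0.8756 − 0.8416) = Φ(0.034) = 0.514.
- r = 0.74, 10%: Φ(0.9405 − 0.8416) = 0.539.

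This was checked by simulating 200,000 trials of 20 patients from correlated gammas (shared-component construction), with the SD of the differences estimated in each trial and the month-12 SD scaled with the mean.

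| True reduction | 0% | 5% | 10% | 15% | 20% |
|---|---|---|---|---|---|
| r = 0.7, normal approximation, equal SDs | 0.20 | 0.34 | 0.51 | 0.68 | 0.82 |
| r = 0.7, simulation | 0.21 | 0.37 | 0.55 | 0.73 | 0.87 |
| r = 0.74, normal approximation, equal SDs | 0.20 | 0.36 | 0.54 | 0.72 | 0.85 |
| r = 0.74, simulation | 0.21 | 0.38 | 0.58 | 0.77 | 0.89 |

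With the month-12 SD equal to baseline, the simulation at 10% gives 0.54 (r = 0.7) and 0.57 (r = 0.74). A gamma-based posterior built as closely as possible to the description in Section 6 gives 0.53 to 0.56 at r = 0.7.

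**Step 4: what would give an 80% chance.** Set effect/SE = 2 × 0.8416.
- At n = 20 the true reduction must be 2 × 0.8416 × 0.1142 = 0.192 (r = 0.7) or 2 × 0.8416 × 0.1063 = 0.179 (r = 0.74).
- At a 10% reduction, n = (2 × 0.8416/0.10)² × 0.6594² × 0.60 ≈ 74 at r = 0.7 with equal SDs.
- At n = 40, the largest row of Table 2, the chance at 10% is 0.65 (r = 0.7) or 0.69 (r = 0.74), by the normal approximation with equal SDs.

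**The case against.** The strongest reply is that nothing printed is wrong. Table 2 is labelled as a posterior probability and never as power, and its 0.50 column tells an attentive reader that these are not rates of meeting a rule. On that reading the sentence only restates that 0.81 is about 4:1 odds. The study is an open-label pilot in a rare disease, its threshold is lenient by design and supports no more than further study, and a Bayesian pilot need not be sized on power. Nor is 10% put forward as the smallest important effect: the only quantified fall in the Background is 20%, in one patient with XLP, and at 20% the chance of meeting the criterion is 0.82 to 0.89.

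Much of this is fair. The table is not miscalculated, and a chance of about one in two, with one in five under no effect, may be acceptable for such a pilot. The upper figure of 0.58 also needs r = 0.74; at the stated r = 0.7 the range is about 0.51 to 0.55. The fit to Table 2 is close but does not prove how the sponsor's code works: 7 of the 35 cells differ by more than 0.0055, all with the formula below the printed value.

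These points do not rescue the sentence. The plan names a threshold, a true effect and a sample size, and says the trial will detect. That asserts how often the rule is met, and the documents give that frequency at no effect size.

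**Conclusion.** The concern holds. Table 2 is sound for the quantity it reports, but it does not support the detection statement drawn from it. With 20 patients and a true 10% reduction the posterior would stay below 80% in roughly 42% to 49% of trials, so the design is close to a coin toss at the effect it names. An 80% chance needs a true reduction of about 18% to 19%, nearly twice that effect.

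The result rests on a flat-prior normal posterior, used because it reproduces Table 2 and because the posterior for α in Section 6 is not specified fully enough to program literally. The choices of month-12 SD, correlation and posterior move the answer by only a few points. All 20 patients are assumed to contribute a month-12 value; fewer would lower the chance further. The figure of about 0.2 under no effect follows directly from an 80% threshold with a non-informative prior. It is not a fault in itself, but it should be stated.

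**What to change.** Keep 20 patients and the 80% threshold, and make three changes.

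1. Relabel Table 2 as the posterior probability that Θ > 0 when the observed d equals the stated effect. If the sponsor's runs computed something else, such as the share of runs with any observed fall, the label should say that.
2. Re-run the simulation: in each run draw a new 20-patient data set, compute the posterior, and count the share of runs at or above 80%. Report this for true reductions of 0, 5, 10, 15 and 20%, at r = 0.7 and r = 0.74, and state the month-12 SD assumed.
3. Replace the detection sentence in Section 6 and the Synopsis with: *With 20 patients, the simulated probability that the posterior probability of Θ > 0 is at least 80% is [__] for a true 10% reduction, [__] for 20% and [__] if iron has no effect (r = 0.7; [__], [__] and [__] at r = 0.74).* Expect roughly 0.5 to 0.6, 0.8 to 0.9 and 0.2. The sponsor's own results should fill the blanks, since the figures here are approximations.

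The cost is wording plus one simulation re-run. If the existing code does not draw a new data set in each run, it needs an outer loop, and the posterior must first be written out in full. The stated performance will look less favourable. No patients, endpoints, thresholds or procedures change.
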